7.2 Date Values

The missing component(s) of incomplete dates (e.g. start and/or stop dates of AE, concomitant medication, medical history) will be assumed as the most conservative value possible. For example, if the start date has a missing day value, the first day of the month will be imputed for study day computations, etc. If day is missing for an end date, the last day of the month will be imputed. If the start date has a missing month value, the first month of the year will be imputed for study day computations, etc. If month is missing for an end date, the last month of the year will be imputed. For determination of treatment-emergent status, the start date will be imputed as the date of the first dose of study drug.

Date imputation will only be used for computational purposes such as treatment-emergent status, etc. Actual data values, as they appear in the original eCRFs, will be presented in the subject data listings.

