If the AE is serious, it should be reported immediately; refer to [Section 6.2.2](#) for SAE reporting requirements and contact information. Other untoward events occurring in the framework of a clinical study are also to be recorded as AEs (i.e., AEs that occur prior to assignment of study treatment and after the signing of the informed consent form (ICF), that are related to a protocol-mandated intervention, including invasive procedures such as biopsies, medication washout, or no treatment run-in).

Any clinically significant signs and symptoms; abnormal test findings; changes in physical examination; hypersensitivity; and other measurements that occur will be reported as an AE.

Laboratory results or test findings will be reported as an AE if the test result requires an adjustment in the study medication(s) or discontinuation of treatment; and/ or test findings require additional testing or surgical intervention; a test result or finding is associated with accompanying symptoms; or a test result is considered to be an AE by the Investigator.

6.1.3 *Handling of Adverse Events*

All AEs should be followed until resolution or stabilization. Subjects must be followed for AEs for 30 calendar days after discontinuation or completion of research study-specific treatment (e.g., chemotherapy, radiation, oral medications, targeted therapy, and surgery) or until the initiation of new therapy for MDS. All new AEs occurring during this period must be reported and followed until resolution unless, in the opinion of the Investigator, the AE or laboratory abnormality/ies are not likely to improve because of the underlying disease.

All adverse events occurring from signing of informed consent to 30 calendar days after completion or discontinuation of protocol-specific treatment, are to be recorded on the appropriate eCRF section.

Once > 30 days have elapsed, only AEs, SAEs, or deaths assessed by the Investigator as treatment-related are to be reported.

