9.3.2 Safety Analysis Endpoints

Safety endpoints will include the incidence of treatment-emergent AEs (TEAEs), characterized and graded using NCI CTCAE v4.03, and changes in laboratory results, ECG findings, physical examinations, vital signs, and ECOG performance status.

Safety will be assessed through the analysis of the reported incidence of TEAEs, including SAEs, dose-limiting toxicities, AEs leading to withdrawal, events of at least CTCAE Version 4.03 Grade 3 in severity, and AEs related to study drug. Treatment-emergent AEs are those with an onset on or after the initiation of therapy. Other safety endpoints include laboratory results, ECG findings, physical examinations, vital signs, and changes in ECOG performance status. A copy of CTCAE Version 4.03 scoring system may be downloaded from:
http://evs.nci.nih.gov/ftp1/CTCAE/CTCAE_4.03_2010-06-14_QuickReference_8.5x11.pdf.

Adverse events will be summarized by Medical Dictionary for Regulatory Activities (MedDRA) coding terms, system organ class, and preferred term for all subjects in the Safety population. The AEs will also be tabulated by maximum severity and relationship to study drug where applicable. Other safety endpoints, including laboratory results, vital signs, and shifts in ECG findings, will be summarized for all subjects in the Safety population. AESIs will be presented also in specific summary table(s) and listing(s).

Concomitant medications will be coded using the WHO-Drug Dictionary and they will be listed and summarized.

The rate of discontinuation, defined as the number of subjects who discontinue study drugs prior to study completion divided by the number of subjects treated, will be calculated for all subjects and for subjects who complete Cycle 3 and Cycle 6.

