2.3 Study Endpoints and Evaluations

2.3.1 Primary Endpoints

The primary efficacy endpoint is overall response rate (ORR) – defined as the proportion of subjects with confirmed complete response (CR) or partial response (PR) according to IWG criteria [1]. The ORRs will be assessed for both stages.

The primary safety endpoint is subject incidence of treatment emergent adverse event (TEAEs).

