10.1 Adverse Events

Treatment-emergent adverse events (TEAEs) will be considered as any event occurring after receiving the first dose of either study drug until 30 days after the last study drug administration.

Treatment emergent adverse events (TEAE) will be classified into a standardized terminology using the Medical Dictionary for Regulatory Activities (MedDRA, version as referenced in the Data Management Plan) System Organ Classifications (SOC) and Preferred Terms (PT), and severity classified according to CTCAE version 4.03. All summaries of the incidence of treatment-emergent adverse events will be provided using the Safety Population for the total group. Although a SOC or PT may be reported more than once for a subject, each subject will only be counted once in the incidence count for that SOC or PT. Summaries of the following types of TEAEs will be provided:

- Overall Summary of Treatment Emergent Adverse Events (TEAEs);
- Summary of TEAEs by MedDRA SOC, PT and Grade (1 or 2, 3 and above);
- Summary of TEAEs related to pracinostat by MedDRA SOC, PT and Grade (1 or 2, 3 and above);
- Summary of TEAEs related to azacitidine by MedDRA SOC, PT and Grade (1 or 2, 3 and above);
- Summary of TEAEs by PT (in descending order)
- Summary of TEAEs leading to discontinuation from the study drug by MedDRA PT, sorted alphabetically by SOC and PT.
- Summary of Treatment Emergent Serious Adverse Events (TESAEs) by MedDRA PT, sorted alphabetically by SOC and PT;
- Summary of TESAEs related to pracinostat by MedDRA SOC, PT and Grade (1 or 2, 3 and above);
- Summary of TESAEs related to azacitidine by MedDRA SOC, PT and Grade (1 or 2, 3 and above);
- Summary of TESAEs by PT (in descending order)
- Summary of TEAEs leading to study treatment interruption
- Summary of TEAEs leading to azacitidine dose reduction

These summaries will present the number and percentage of subjects reporting an adverse event for each classification level. The denominators for calculating the percentages will be based on the number of exposed subjects in the Safety Population (i.e., study drug was administered) in the total group.

All adverse events, serious adverse events and deaths, and adverse events leading to discontinuation from the study will also be provided in data listings by subject.

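### SAP 7.2, read literally, gives every adverse event with an incomplete start date the first-dose date for treatment emergence, with no exception where the recorded month, year or stop date shows onset before Day 1

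*SAP*

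**What the plan says.** SAP 7.2 opens with a general principle: missing parts of an incomplete date "will be assumed as the most conservative value possible". It then gives rules by component. For example, "if the start date has a missing day value, the first day of the month will be imputed for study day computations, etc". A missing start month is set to the first month of the year, and end dates go to the last day or last month.

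A separate sentence covers treatment emergence: "For determination of treatment-emergent status, the start date will be imputed as the date of the first dose of study drug". It sets no condition on the known month or year, or on the stop date. The section adds that "Date imputation will only be used for computational purposes such as treatment-emergent status, etc", and that listings show the values as recorded.

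The definitions this rule feeds are:

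- Protocol 9.3.2: "Treatment-emergent AEs are those with an onset on or after the initiation of therapy".
- SAP 10.1: "any event occurring after receiving the first dose of either study drug until 30 days after the last study drug administration".
- SAP 2.3.1 makes the incidence of treatment-emergent adverse events (TEAEs), counted by subject, the primary safety endpoint.

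The protocol gives two answers on whether pre-dose events are recorded at all. Section 6.1.2 starts recording at the start of study drug, and adds earlier events only where they relate to a protocol-mandated procedure. Section 6.1.3 requires "All adverse events occurring from signing of informed consent to 30 calendar days after completion or discontinuation of protocol-specific treatment" to be recorded. Protocol 5.1 and Appendix A schedule an adverse event assessment at screening.

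For medications, SAP 10.5 treats a partial date as concomitant only when the date cannot settle the category.

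**The concern.** Using the first-dose date is a sound default when the recorded parts leave open whether onset came before or after dosing. The sentence in 7.2 does not stop there. Taken literally, it also overrides recorded evidence that the event began, or even ended, before Day 1, and such an event can be given an onset later than its own resolution.

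The trial has one arm, so no control group carries the same error for comparison. Event rates by term will be read as the rates on pracinostat plus azacitidine, and pre-dose events counted among them would be attributed to treatment. The wording also leaves room for two programmers to implement 7.2 differently and reach different tables.

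**Working it through.** The documents attach no figure to this rule, so there is none to reproduce. The check applies the rule to constructed records and then bounds the size of the effect.

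**1. The rule applied.** Assume first dose 5 March 2019 and last dose 1 June 2019. The SAP 10.1 window then ends 30 days later, on 1 July 2019. Three readings are compared:

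- *Literal*: any incomplete start date becomes 5 March.
- *Narrow*: only the missing day is taken from the first-dose date; the known month and year are kept.
- *Conditional*: the first-dose date is used only where the known parts and the stop date leave the order open.

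| Recorded start and stop | Literal | Narrow | Conditional |
|---|---|---|---|
| Feb 2019, day missing; stop 28 Feb | 5 Mar, TEAE | 5 Feb, not TEAE | not TEAE |
| Feb 2019, day missing; no stop date | 5 Mar, TEAE | 5 Feb, not TEAE | not TEAE |
| Mar 2019, day missing; stop 3 Mar | 5 Mar, TEAE | 5 Mar, TEAE | not TEAE |
| Mar 2019, day missing; ongoing | 5 Mar, TEAE | 5 Mar, TEAE | TEAE |
| Sep 2019, day missing | 5 Mar, TEAE | 5 Sep, not TEAE | not TEAE |

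The literal rule counts all five. The first three are shown by their own recorded data to be pre-dose. The fifth lies outside the SAP 10.1 window. Only the fourth is open, and every reading counts it. The narrow reading corrects the records with an earlier month but still fails on the third, where onset falls after the stop date.

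**2. How often the month alone settles the question.** Suppose pre-dose onsets are spread evenly over the W days before Day 1. An onset k days earlier falls in a previous calendar month for about k/30.4 of Day 1 dates (mean month length 365/12 = 30.4). Averaging over k = 1 to W gives (W + 1)/2 ÷ 30.4:

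- W = 7: 4/30.4 = 13%.
- W = 14, the screening window in SAP 7.1: 7.5/30.4 = 25%.
- W = 28: 14.5/30.4 = 48%.

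Enumerating every Day 1 over two years gives 13.2%, 24.7% and 47.7%. Recorded stop dates would settle more cases. These are shares of pre-dose records with a missing day, and the documents do not give the number of such records.

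**3. Effect on one term.** Take N = 60 as an assumed denominator; the plan's figure is approximately 60 efficacy-evaluable subjects, and the Safety Population may differ. One wrongly counted subject adds 1/60 = 1.7 points. Starting from 3 true cases, with exact 95% intervals:

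- None added: 3/60 = 5.0% (1.0 to 13.9).
- One added: 4/60 = 6.7% (1.8 to 16.2).
- Three added: 6/60 = 10.0% (3.8 to 20.5).

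Nothing is added if the subject also has the same term on treatment, because SAP 10.1 counts each subject once per term.

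**The case against.** **The text allows a narrower reading.** The paragraph opens by imputing only missing components, so a known month could be taken as kept. That reading is available. But the treatment-emergence sentence speaks of the start date as a whole and does not say that known parts are retained, and the narrow reading still ignores the stop date. The section is ambiguous at best.

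**The rule is conservative.** It errs towards reporting more harm, in line with the stated principle, and a separate rule is needed. First-of-month imputation would date the ongoing March record to 1 March and drop a possible TEAE. This defends the default for open dates. It does not justify overriding recorded dates.

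**Few records may be affected.** This largely stands. Protocol 6.1.2 and 6.1.3 disagree on whether pre-dose events are recorded. Protocol 6.3.6 sends preexisting conditions to medical history unless they worsen, and SAP 10.10 does the same for clinically significant screening examination findings. Baseline signs and symptoms are a separate screening item. A reader might infer that fatigue, infection, bleeding or cytopenia from existing MDS would be reported as emerging on treatment. The documents do not support that as the usual outcome. What remains is mainly new events during screening that are entered as adverse events without a full start date.

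**The primary safety endpoint is hardly touched.** A reader might infer that the headline incidence is materially inflated. A misdated event changes the share of subjects with any TEAE only if the subject has no other TEAE. Protocol 1.4 lists fatigue, gastrointestinal effects and myelosuppression as the most common side effects, so few such subjects are likely.

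**Late events are a weak argument.** The September record conflicts with SAP 10.1. Protocol 9.3.2 has no upper time limit, however, and beyond 30 days protocol 6.1.3 asks only for treatment-related events. Nor is it a fault in itself that one event carries different imputed dates for different computations.

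**Conclusion.** The point holds as a wording defect with a small expected effect. As written, SAP 7.2 can class an event as treatment-emergent when its own recorded dates show it was not, contrary to protocol 9.3.2 and SAP 10.1. SAP 10.5 shows that the plan already has the right form of rule for medications.

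Only adverse events with incomplete start dates are affected; fully dated pre-dose events are classified correctly. The size is at most 1.7 points per wrongly counted subject per term, assuming 60 subjects. It falls mainly on the tables by system organ class, preferred term, grade and relatedness. The total effect cannot be computed, because the documents give no count of partial dates. The 25% is a calendar fraction under an assumed even spread of onsets and should not be read as an error rate. A claim that the primary safety endpoint is materially biased would go beyond what the documents show.

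**What to change.** Replace the treatment-emergence sentence in SAP 7.2 with:

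> For treatment-emergent status, an incomplete start date is set to the first-dose date only if its known parts (month and year, or year alone if the month is missing) match those of Day 1, or the date is wholly missing, and the stop date is not before Day 1. Otherwise the known parts of the start date and any stop date determine the status. Events whose status these data leave open are treated as treatment-emergent.

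The year-only clause is needed because a rule based on month and year cannot classify a date with only the year recorded. The last sentence covers a known month that straddles the end of the 30-day window. Partial stop dates can use the end-of-month and end-of-year rules already in 7.2.

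The sponsor should also reconcile protocol 6.1.2 and 6.1.3 on when recording starts, since that decides how many pre-dose records can exist.

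The cost is a short SAP rewording and a routine programming condition, with no new data collection. It should be done before database lock.

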7.3 Other Missing Values

Every effort will be made to obtain required data at each scheduled evaluation from all subjects who have been enrolled. There will be no imputation for missing data.

7.4 Data Derivations

Baseline values will be considered as the last non-missing assessment prior to the first administration of either study drug (pracinostat or azacitidine). Assessments performed prior to Day 1 for all other study procedures will be assumed to have been performed prior to administration of either study drug. Unless otherwise specified, change from baseline (CFB) calculations for a treatment window assessment will be the applicable treatment window assessment minus the baseline assessment (i.e., $CFB = \text{treatment window assessment} - \text{baseline}$). If either the treatment window assessment value or the baseline value is/are missing, then CFB will be set to missing.

For a given date within the screening window, Study Day will be computed as the given date minus Day 1 (i.e., $\text{Study Day} = \text{Date} - \text{Day 1}$).

For a given date within the treatment window, Study Day will be computed as the given date minus Day 1 plus 1 (i.e., $\text{Study Day} = \text{Date} - \text{Day 1} + 1$).

Age will be calculated from the date of birth to the date of informed consent.

The following will define prior medication use versus concomitant medication use:

- Prior: Medication use ended before Day 1;
- Concomitant: Medication use (initiation date, or the stop date) is on or after Day 1.

8 STUDY POPULATION

Unless otherwise stated, all study population analyses will be performed using the ITT Population (see Section 5.2). Subjects who are approved by the Medical Monitor, but never dosed are not included in listings such as “Demographics” and instead only included in a table of Screen Failures or Subjects excluded from analysis populations. Unless otherwise stated, summaries will be summarized in a total group.

8.1 Subject Enrollment

Subject enrollment will be summarized as the number and percentage for each analysis population overall. Subjects who were never dosed will not be included in “enrolled”. The denominators for calculating percentages will be based on the number of enrolled subjects.

A summary of the number of subjects who were screen failures along with the reasons for screen failure will be provided overall. The number of subjects enrolled but never treated will be provided for the total group.

Enrollment information will be provided in a data listing by subject.

8.2 Subject Disposition

Subject disposition will be presented for the ITT population using descriptive statistics. The number and percentage of subjects who receive at least one dose of study drug (pracinostat or azacitidine), subjects who have completed the study versus discontinued from the study, and subjects who discontinued from the study with their accompanying reason for discontinuation summarized for the total group. The denominators for calculating percentages will be based on the number of subjects for the total group.

Subjects who discontinued prior to dosing will be excluded from the analysis and treated as a screen failure. Discontinued subjects will be provided in a data listing by subject.

8.3 Protocol Deviations

Major protocol deviations are defined to be those deviations that could potentially bias either efficacy or safety summaries of the study. Subjects associated with major protocol deviations will be identified and documented prior to database lock.

Major deviations from the clinical protocol may include, but are not limited to:

- Informed consent issue
- Inclusion/exclusion criteria “other than those pre-planned via a waiver”
- Protocol required evaluation not completed
- Non-compliance with study drug administration
- Received excluded treatment or prohibited medication
- Developed withdrawal criteria but not withdrawn

The number and percentage of subjects with major deviations and the number of deviations will be summarized by type of deviation and overall. Summaries will be provided for the total group. The denominators for calculating percentages will be based on the number of subjects in the ITT population for the total group.

All protocol deviations not classified as major protocol deviations will be classified as minor protocol deviations.

All protocol deviations will be provided in a data listing by subject.

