4 SUBJECT POPULATION AND DISCONTINUATION CRITERIA

4.1 Inclusion Criteria

To be eligible for study participation, subjects must meet the following inclusion criteria:

1. Female or male subjects ≥ 18 years-of-age.
2. Histologically or cytologically documented diagnosis of MDS according to the World Health Organization (WHO) classification ([Vardiman 2009](#), [Arber 2016](#); [Appendix B](#)) with $< 20\%$ bone marrow blasts by morphology and a peripheral white blood cell (WBC) count of $< 20,000/\mu\text{L}$.
 - If WBC $\geq 20,000/\mu\text{L}$, cytoreduction with hydroxyurea is permitted prior to enrollment.
 - CMML-1 and CMML-2 subtypes are eligible for study participation.
3. Classified as high or very high risk according to the Revised International Prognostic Scoring System (IPSS-R) risk category ([Appendix C](#)). CMML-1 and CMML-2 subtypes will be considered high-risk MDS and will not require IPSS-R scoring.
4. Bone marrow biopsy (BMBx) and/or aspirate within 28 days prior to planned first study treatment.

5. Clinical indication for treatment with azacitidine.
6. Previously untreated with HMAs (prior therapy with transfusions, hematopoietic growth factors, or immunosuppressive therapy is allowed).
 - Subjects who require start of an HMA (e.g., azacitidine) due to progressing MDS may receive up to 1 cycle of azacitidine within 30 days prior to Cycle 1 Day 1.
7. ECOG performance status of 0, 1, or 2.
8. Adequate organ function as evidenced by:
 - Aspartate aminotransferase (AST) and alanine aminotransferase (ALT) $\leq 2.5 \times$ the upper limit of normal (ULN).
 - Total bilirubin $\leq 1.5 \times$ ULN or total bilirubin of ≤ 2 mg/dL, whichever is higher. Total bilirubin $< 3 \times$ ULN for patients with Gilbert-Meulengracht Syndrome.
 - Serum creatinine $\leq 1.5 \times$ ULN, or creatinine clearance ≥ 40 mL/min according to institutional standards (actual body weight should be used to calculate creatinine clearance).
 - QTcF interval ≤ 450 msec using the mean of triplicate electrocardiograms (ECGs).

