5.3 Per Protocol (PP) Population

The Per Protocol (PP) population is defined as all treated subjects without major protocol deviations, as detailed in section 8.3. The PP population will be used for the primary efficacy analysis.

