13 CHANGES FROM PROTOCOLLED ANALYSIS

The protocol states that the definition of overall survival is time from the first day of study drug administration (day 1) to death from any cause on study. Subjects who are alive will be censored at the date of last disease evaluation. This has been changed to the standardly used definition of time from the first day of study drug administration (day 1) to death from any cause on study. Subjects who are alive will be censored at the date of last visit or contact with the investigator.

The per protocol population has been renamed as the efficacy evaluable population, and an additional population, named the per protocol population, has been included in order to perform a sensitivity analysis excluding patients with major deviations.

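### The waiver exemption in SAP 8.3 lets a subject who failed an eligibility criterion stay in the per-protocol set by default, although the protocol has no waiver process

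*SAP*

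**What the plan says.** SAP 8.3 (Protocol Deviations) gives a general test: "Major protocol deviations are defined to be those deviations that could potentially bias either efficacy or safety summaries of the study". It then offers examples, introduced by "Major deviations from the clinical protocol may include, but are not limited to". One example is inclusion/exclusion criteria, limited to those "other than those pre-planned via a waiver". No other item on the list has an exemption. The section closes the classification with "All protocol deviations not classified as major protocol deviations will be classified as minor protocol deviations".

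SAP 5.3 (Per Protocol Population) takes its membership from there: PP "is defined as all treated subjects without major protocol deviations, as detailed in section 8.3". SAP 13 explains that this population was added "in order to perform a sensitivity analysis excluding patients with major deviations".

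The protocol treats eligibility as mandatory. Section 4.1 opens with "To be eligible for study participation, subjects must meet the following inclusion criteria", section 4.2 excludes anyone who fails an inclusion criterion or meets an exclusion criterion, and footnote d to the Schedule of Events in Appendix A requires the criteria to be met before enrollment.

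**The concern.** A waiver is an agreement to enroll someone who does not fit the criteria. It does not make that person part of the target population, and it does not alter whether the violation could bias the response rate, which is SAP 8.3's own test. Exempting waived violations therefore works against the reason SAP 13 gives for having a PP set.

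PP is one of the checks on the primary overall response rate (ORR). If waived subjects remain in it, PP can agree with ITT partly because both contain the same ineligible subjects. SAP 9 also drops the PP tables when PP and ITT are identical. If waived violations were the only ones that would otherwise have been major, the exemption would make the two sets identical and no PP table would be produced.

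There is a smaller reporting gap. The summary by type in SAP 8.3 (Table 14.1.4) covers major deviations only, so waived violations classed as minor would appear in subject listings but not in a count.

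**Working it through.** **Text check**

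1. An eligibility violation under a waiver is carved out of the listed examples of major deviations (SAP 8.3).
2. A deviation not classed as major is minor (SAP 8.3).
3. PP removes only subjects with major deviations, by reference to 8.3 (SAP 5.3, Per Protocol Population).
4. So, unless someone classes the violation as major under the general test, the subject stays in PP.

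**Is there a waiver process for the exemption to refer to?** None appears in Protocol 4.1, 4.2 or Appendix A. The one case-by-case clause is in exclusion criterion 10, where other malignancies may be considered after consulting the Medical Monitor. That discretion is part of the criterion, so using it is not a deviation and needs no waiver. SAP 8.3 does not say who may grant a waiver, for which criteria, or how it is recorded, and SAP 13 does not list waivers among the changes from the protocol.

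**Size, under assumed counts**

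Inputs from the documents: N = 60 and a design ORR of 40%, i.e. 24 responders, with a lower 95% limit of 27.6% (SAP 4.2); exact binomial intervals (SAP 9.1); azacitidine-alone ORR of about 25% (SAP 4.2). Assumed, because the documents give no count: w = 2 to 5 waived subjects among 60 treated, and no other major deviations.

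The plan's figure first. The exact lower limit is the 2.5% quantile of a Beta(x, n − x + 1) distribution. For x = 24 and n = 60 it is 27.56%, which reproduces 27.6%.

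If r of the w waived subjects responded, PP without them has

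ORR = (24 − r) / (60 − w), and shift from 40% = (0.4w − r) / (60 − w).

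| w | r | PP without waived subjects | Shift (points) | Exact lower 95% limit |
|---|---|---|---|---|
| 0 | 0 | 24/60 = 40.0% | 0 | 27.6% |
| 2 | 0 | 24/58 = 41.4% | +1.4 | 28.6% |
| 2 | 1 | 23/58 = 39.7% | −0.3 | 27.0% |
| 2 | 2 | 22/58 = 37.9% | −2.1 | 25.5% |
| 3 | 3 | 21/57 = 36.8% | −3.2 | 24.4% |
| 5 | 0 | 24/55 = 43.6% | +3.6 | 30.3% |
| 5 | 2 | 22/55 = 40.0% | 0 | 27.0% |
| 5 | 5 | 19/55 = 34.5% | −5.5 | 22.2% |

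The shift is zero when the waived subjects respond at the same 40% rate as the rest, and it reaches 5.5 points only if all five responded. The plan's argument is that the lower limit lies above about 25%. Three waived subjects, all responders, would be enough to take the PP lower limit below that.

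**The case against.** The exemption is not the governing rule. SAP 8.3 defines a major deviation by its potential to bias the summaries, and its list is expressly incomplete. A waived subject with, say, 20% or more marrow blasts could still be classed as major before database lock. This stands, and it rules out the reading that waived subjects are certain to remain in PP. Retention is the default, and the only text that addresses waivers favours it.

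A reader might also infer that the sponsor alone decides, subject by subject and with responses in view, who counts as eligible. The documents do not support that. They do not say who grants a waiver, SAP 12 has both the sponsor and the CRO sign off on deviation classifications, and a waiver planned in advance would ordinarily precede any response. The issue is who belongs in the target population, not selection on outcome.

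Little depends on PP. Protocol 9.2 and SAP 9 use ITT for efficacy, SAP 13 calls PP a sensitivity analysis, and SAP 6.5 plans no hypothesis tests. This stands too. SAP 5.3 does assign PP to the primary efficacy analysis, but that is a separate inconsistency and this point does not rest on it.

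The violations would not be hidden. SAP 8.3 and 8.4 list all deviations and all eligibility deviations by subject, and SAP 8.5 and 8.6.3 report baseline IPSS-R and prior MDS therapy. Only a count of waived subjects is missing.

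Finally, treating every unmet criterion as major would go too far. A marrow sample taken one day outside the 28-day window need not bias anything, and such a rule would conflict with 8.3's own test. The fix below respects this.

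**Conclusion.** The point holds as a minor one. As written, SAP 8.3 steers waived eligibility violations towards the minor class and so into PP, with no waiver process in the protocol behind it and against the purpose stated in SAP 13.

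The effect is conditional. The documents do not show that any waiver was granted; if none was, nothing changes. ITT results are unaffected in every case. With 2 to 5 waived subjects in 60 and 24 of 60 responders, both assumed for illustration, the PP ORR would shift by 0 to 5.5 points.

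SAP 13 also does not say that PP exists specifically to remove ineligible subjects, as a reader might infer. It says major deviations in general, of which eligibility violations are one listed type.

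**What to change.** In SAP 8.3, delete "other than those pre-planned via a waiver" and add a sentence stating that a prior waiver does not change the classification. An eligibility violation that could bias the efficacy or safety summaries (for example in risk category, prior hypomethylating-agent exposure or blast percentage) is major and removes the subject from PP, waived or not. Violations without that potential stay minor under the existing test.

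Alongside Table 14.1.4, report the number of waived eligibility violations by criterion, including zero if there were none.

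The cost is one deleted phrase, one added sentence and one extra count from deviation data already planned for listing. PP may be slightly smaller.
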